### 9.2 Data Management

Data that are collected for this study will be kept in an electronic database hosted in a secure data center. Access to the de-identified study data will be limited to study personnel at NS Health and to the sponsor. Access to the data will be role-based, with specific permissions assigned to each role. Access to the study data will be through login credentials that are specific to the individual and access will be tracked via audit logs. Study data will be encrypted at rest. Access to the study database is via a secure web portal and data are encrypted in transit.

Paper documents such as completed subject questionnaires will be stored at NS Health in a secure location to which only study personnel have access.

The image data collected for the study – the treatment planning fan-beam CT, the TrueBeam CBCT and the Ethos CBCT – will be exported from the clinical systems on which they were acquired and stored in a secure folder behind NSHA firewalls accessible only to the study investigators and co-investigators. Images will be de-identified on export. The de-identified image data collected in this study will be shared with the study sponsor, Varian Medical Systems. De-identified image data will be transferred to secure data storage hosted by Varian via secure web upload. Access to the image storage will be limited to study personnel at NSHA and personnel at Varian. As with the study database, access to the image storage is by login credentials (username and a password) that are unique to the individual.

De-identified images will be uploaded to the MeVis system for qualitative evaluation. These images will be deleted from the MeVis system when the study is complete.

## 10 STATISTICAL CONSIDERATIONS

### 10.1 Sample Size

The study design does not involve any intervention in the subject's cancer care. The study is being performed to assess the image quality in a new CBCT system.

This study will accrue thirty (30) subjects, which will include:

- A minimum of 7 subjects with liver cancer
- A minimum of 7 subjects with lung cancer
- A minimum of 7 subjects with cancer in the left breast

Subjects with other cancers can be included so long as the patients meet the study's inclusion/exclusion criteria.

Seven subjects in each cohort will provide sufficient image data for a range of subject variation in the same anatomical site.

Data will be collected and analyzed as described in Section 5. Quantitative image quality metrics for the different imaging modalities will be compared using average values and standard deviations. Qualitative evaluations of image quality using a Likert scale will be compared using a Mann-Whitney test. Dosimetry will be compared using average values of metrics derived from dose-volume histograms and standard deviations of those values. Patient experience of the different CBCT acquisitions will be compared qualitatively based on responses to questionnaires.

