## 5 Research Plan

### 5.1 Study Methodology

1. The methodology for treatment setup, CT simulation, treatment planning, image guidance and treatment delivery will be determined by the patient's treatment team and is not specified in this protocol. Enrollment in the study may occur after treatment delivery has started but must be prior to the fifth fraction.
2. Following completion of informed consent to participate in this study, the Ethos imaging will be scheduled immediately before or after one of the subject's first five scheduled treatment fractions. While there will be some flexibility in scheduling the session on Ethos, it will be advantageous for the study imaging to be performed as soon as possible after the CT simulation to minimize the potential for anatomical change over time. Two research CBCT images will be acquired, one with breath hold, the other with free breathing.

The Ethos unit will be installed in the same department as the patient's treatment unit therefore the acquisition of the additional study imaging will not require a separate visit. We anticipate the study imaging will require no longer than 15 minutes. No treatment delivery will take place on the Ethos unit during this study.

3. The patient's CT simulation data, TrueBeam CBCT image data and Ethos CBCT data will be exported from the treatment planning system(s) for comparative analysis of image quality as detailed below. The TrueBeam CBCT used in the analysis will be exported from the treatment session delivered on the same day that the Ethos CBCTs are acquired. Data will be anonymized during the export process. Exported image data will be stored in a password-protected folder on the network drive behind hospital firewalls.

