### 5.2 Analysis of data

1. Image quality will be quantified by calculating contrast-to-noise ratio (CNR), spatial resolution, Hounsfield Unit accuracy, and presence/absence of artifacts in each of the four image datasets acquired for each subject. This will be done using analysis scripts developed in MATLAB and the Eclipse API (ESAPI, Varian Medical Systems) in the Nova Scotia Health Department of Medical Physics.

CNR will be quantified using

$$\text{CNR} = (|\langle P_{\text{ROI}} \rangle - \langle P_{\text{BG}} \rangle|) / (S_{\text{ROI}}^2 + S_{\text{BG}}^2)^{0.5}$$

where  $\langle P_{\text{ROI}} \rangle$  and  $\langle P_{\text{BG}} \rangle$  are the mean Hounsfield Units (HU) in a selected region of interest and proximal background region, respectively, while  $S_{\text{ROI}}$  and  $S_{\text{BG}}$  are the standard deviations of the HU values in the corresponding regions.

Spatial resolution will be assessed by comparing HU profiles of high-contrast detail in image sets. Artifacts will be assessed qualitatively.

2. The patient's treatment plan, which is originally calculated on the fan-beam CT dataset (as per standard protocol) will be recalculated on both the TrueBeam CBCT and Ethos CBCT datasets using the following process: Target volumes and organ-at-risk contours that are relevant to the anatomy being imaged will be transferred from the original treatment plan onto the CBCTs through an elastic deformation. The accuracy of the contour registration will be verified by a radiation oncologist and contours will be adjusted manually, if necessary, to ensure proper alignment with the underlying image prior to re-calculation of the dose distribution. The dose volume histograms from the original treatment plan will be compared to those generated from the three CBCT-based plans in terms of standard dosimetry metrics, i.e., target volume coverage and organ-at-risk sparing.

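### The quantitative primary metrics are summarised by modality mean and SD, with no within-patient difference or interval, although every subject supplies all four image sets

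*Combined protocol and SAP*

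**What the plan says.** Section 2.1 makes the primary objective comparative. It implies four contrasts: Ethos with breath hold and Ethos under free breathing, each against fan-beam CT and each against TrueBeam CBCT.

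Section 5.2, item 1, computes the image metrics "in each of the four image datasets acquired for each subject". The four are fan-beam CT, TrueBeam CBCT and the two Ethos CBCTs. Section 5.1 ties the two CBCT systems together in time: "The TrueBeam CBCT used in the analysis will be exported from the treatment session delivered on the same day that the Ethos CBCTs are acquired".

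The only analysis rule for the numeric metrics is in section 10.1: "Quantitative image quality metrics for the different imaging modalities will be compared using average values and standard deviations". Neither section 5.2 nor section 10.1 mentions a paired difference, an SD of differences, a confidence interval or a model for these metrics. The one named test, Mann-Whitney, is reserved for Likert scores.

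On the sample, section 10.1 states "This study will accrue thirty (30) subjects, which will include" at least seven subjects each with liver, lung and left breast cancer, and adds "Subjects with other cancers can be included so long as the patients meet the study's inclusion/exclusion criteria". The size is justified by "Seven subjects in each cohort will provide sufficient image data for a range of subject variation in the same anatomical site". The plan says neither that the metrics are pooled over sites nor that they are analysed by site.

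Section 5.2 assesses artifacts qualitatively, so the point covers CNR, HU accuracy and any numeric resolution measure.

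**The concern.** The design collects matched data, but the analysis sentence does not say that the matching will be used. Followed literally, it gives a table with one mean and one SD per modality. Such an SD contains everything that makes patients differ: body habitus, the chosen region and its background and, if sites are combined, the native contrast of different anatomy. The question in section 2.1 is how far two systems differ in the same patient. The uncertainty of that difference depends on how closely a patient's two values track each other, and the table does not show this.

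Two systems could therefore appear to overlap widely although one is consistently better in almost every patient. A reader of the results could not correct for this, because the correlation cannot be recovered from the two SDs.

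HU accuracy has a further gap. Section 5.2 gives no reference value for it and does not say whether errors are taken with or without sign.

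**Working it through.** **Inputs from the documents.** n = 30; minimum of 7 in each of three sites (section 10.1); four image sets per subject (section 5.2). The minima fit the total: 3 × 7 = 21, leaving 30 − 21 = 9 subjects of any eligible site. Section 10.1 gives no alpha, power, effect size, SD or precision target, so there is no statistical derivation of 30 to reproduce.

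**Assumptions.** Equal SD for each modality, taken as 1; two-sided 95% intervals; within-subject correlation ρ between modalities, not given in the documents, shown from 0 to 0.9.

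**Point estimate.** With complete data, the difference between two modality means equals the mean of the within-subject differences. Pairing does not change it.

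**Precision.** For two modalities with SDs s₁ and s₂, the variance of the within-subject difference is s₁² + s₂² − 2ρs₁s₂. With both SDs equal to 1 this is 2(1 − ρ).

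- Pairing ignored: SE = √(2/30) = 0.258; half-width = t(58) × 0.258 = 0.52 SD.
- Pairing used: SE = √(2(1 − ρ)/30); half-width = t(29) × SE.

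| ρ (assumed) | SE, paired | Half-width, n = 30 | SE relative to ignoring pairing, √(1 − ρ) |
|---|---|---|---|
| 0 | 0.258 | 0.53 | 1.00 |
| 0.3 | 0.216 | 0.44 | 0.84 |
| 0.5 | 0.183 | 0.37 | 0.71 |
| 0.7 | 0.141 | 0.29 | 0.55 |
| 0.9 | 0.082 | 0.17 | 0.32 |

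At ρ = 0 pairing gains nothing.

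**One cohort of seven.** The same formulas with n = 7 give 1.16 SD with pairing ignored, and 1.09, 0.92, 0.72 or 0.41 SD paired at ρ = 0.3, 0.5, 0.7 or 0.9. By-site results are therefore imprecise either way and should be read as descriptive.

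**Effect of site.** Assume a between-patient SD within a site of 1, a within-patient SD of 0.5, and a between-site SD of 0, 1 or 2. If sites were combined, the per-modality SD would be √(1 + 0 + 0.25) = 1.12, √(1 + 1 + 0.25) = 1.50 or √(1 + 4 + 0.25) = 2.29. The SD of the paired difference is √(2 × 0.25) = 0.71 in all three cases. Even with no site effect, the per-modality SD is not the quantity needed; combining sites widens the gap.

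**The case against.** The best defence is that the sentence in section 10.1 is under-specified rather than unpaired. Averages and SDs could be those of within-patient differences, and the background in section 1.1 and the same-day rule in section 5.1 both suggest a comparison patient by patient. That stands as far as it goes: the wording does not exclude it. The neighbouring text points the other way, however. The parallel sentence on dosimetry refers to SDs of the metric values themselves, and the only test named anywhere in the plan is one for independent samples.

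It is also fair that this is a single-site feasibility study meant to describe image quality. No alpha, power or decision rule is attached to these metrics, so none is broken. All per-subject values are kept, so paired summaries can be added without changing data collection. This bears on how serious the point is, not on whether it is correct.

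A reader might infer more than the documents support:

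- *That the metrics are pooled over tumour sites.* The plan is silent. The minimum of seven per site and the reference to variation within one anatomical site leave by-site summaries open.
- *That the plan yields no estimate of the modality effect.* With complete data it does; only the precision is missing. If scans are missing, the modality means would rest on partly different patients.
- *That a significance test would miss a real gain.* No test is planned for these metrics.
- *That HU errors of opposite sign will cancel.* Signed averaging is not stated, and an SD reported beside a near-zero mean would show the spread. What is missing is a definition.

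**Conclusion.** The point holds in this form: the plan does not state that the quantitative modality comparisons are within-patient, provides no valid measure of precision for the four primary contrasts, and does not say how tumour site enters. Ignoring the pairing leaves the estimate unchanged, but the standard error would be overstated by a factor of 1/√(1 − ρ): about 1.2 at a correlation of 0.3 (1/0.837) and about 3.2 at 0.9 (1/0.316). The size rests on the assumed correlation, on equal SDs across modalities and on all 30 subjects having complete data. The direction needs only a positive correlation, which is plausible for scans of the same patient but is not documented. The label is free improvement.

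**What to change.** Amend section 10.1, with a matching line in section 5.2, item 1:

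- **CNR (log scale) and any numeric resolution measure.** For each of the four contrasts in section 2.1, report the mean within-subject difference with its SD and 95% confidence interval; back-transform CNR to a ratio. Give the result overall and, descriptively, by tumour site. A mixed model with modality and site as fixed effects and subject as random effect serves the same purpose. Site-specific estimates then need a modality-by-site term, because a site main effect alone does not alter a within-subject contrast when data are complete.
- **HU accuracy.** Report each CBCT's signed and absolute deviation from the same subject's fan-beam CT in matched tissue regions, with 95% confidence intervals. Compare Ethos with TrueBeam on the within-subject difference in absolute deviation. Both forms are needed: absolute deviation loses the direction of bias and, since fan-beam deviates from itself by zero, cannot be negative in a contrast with fan-beam.
- **Existing summary.** Keep mean and SD per modality as a supplementary table.

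The cost is analysis wording and a small amount of code. No additional patients, scans or readers are needed.

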### 2.2 Study Endpoints/Metrics

#### 2.2.1 Primary Objective Metrics

The quality of fan-beam CT, Truebeam CBCT, and Ethos CBCTs will be compared quantitatively using the following calculated metrics:

- Contrast-to-noise ratio (CNR)
- Resolution
- Hounsfield Unit (HU) accuracy
- Artifact reduction

Furthermore, the three image sets will be evaluated qualitatively by multiple observers with training in radiation oncology and image-guided radiation therapy, who will rank the images acquired for each subject by perceived quality/usefulness for structure contouring and RT guidance.

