3. Anonymized fan-beam CT images, status-quo CBCT image and Ethos CBCT image data sets (with breath hold and with free breathing) will be presented to multiple observers for qualitative assessment of perceived image quality. Observers will include up to five radiation oncologists and five radiation therapists, who will answer questions on image quality for contouring and image guidance purposes, respectively. Image quality will be scored either as a simple ranking (1 to 3) or using a five-point Likert scale. This review will be done using the MeVis framework (see example, Figure 2) that allows centralized user management and authentication, ensuring controlled access to data with unique login credentials for each individual. In the case of Likert scale ranking, analysis will be performed using a Mann-Whitney test.

[figure not shown]

Figure 2 Example of qualitative image review using the MeVis framework.

4. A patient experience questionnaire will be provided to each subject on the day they undergo CBCT imaging on the Ethos platform. Subjects will be encouraged to fill out the questionnaire on that day. Study coordinators will transcribe subject responses into the study database.

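### If readers score on the Likert scale, the planned Mann-Whitney test ignores that the scores are paired within subject and clustered by reader

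*Combined protocol and SAP*

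**What the plan says.** Section 2.2.1 makes reader assessment part of the primary objective. It describes observers "who will rank the images acquired for each subject by perceived quality/usefulness for structure contouring and RT guidance". Section 5.2(1) refers to "each of the four image datasets acquired for each subject", namely planning fan-beam CT, TrueBeam CBCT, Ethos CBCT with breath hold and Ethos CBCT in free breathing. Section 5.2(3) sends the same sets to the readers. On numbers it says "Observers will include up to five radiation oncologists and five radiation therapists"; oncologists judge contouring and therapists judge image guidance.

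The scale is left open: "Image quality will be scored either as a simple ranking (1 to 3) or using a five-point Likert scale". A test is named for one branch only: "In the case of Likert scale ranking, analysis will be performed using a Mann-Whitney test". Section 10.1 repeats that choice: "Qualitative evaluations of image quality using a Likert scale will be compared using a Mann-Whitney test". Neither section mentions pairing, averaging over readers, a mixed or ordinal model, a Friedman or signed-rank test, a significance level or a multiplicity rule.

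**The concern.** Mann-Whitney compares two groups of mutually independent observations. These scores depart from that in two ways. The image sets being compared come from the same people, so scores for different sets share a subject effect. Several readers also score the same image, so their scores on it are correlated.

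The two departures push the error in opposite directions. Ignoring the pairing leaves between-subject variation in the noise, which makes p-values too large. Counting several readings of one image as separate observations overstates the information, which makes p-values too small. The plan does not say how scores are to be arranged, so the reader of a p-value could not tell which error dominates.

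This is the only hypothesis test the plan names. Section 10.1 compares quantitative image quality and dosimetry by means and standard deviations, and patient experience qualitatively. The test also takes two groups at a time, while section 2.1 implies four contrasts among four image sets.

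**Working it through.** **Plan's own figure.** There is none to reproduce. The plan gives no significance level, power, expected effect or variance for the scores, and 30 subjects is justified by coverage of subject variation.

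**Inputs from the plan.** S = 30 subjects (10.1), R up to 5 readers per discipline and a five-point scale (5.2(3)), four image sets (5.2(1)).

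**Assumptions.** Two-sided 5% level; every reader in a discipline scores every subject; a latent normal score cut into five categories. The latent score is the sum of subject (s), reader (r), subject-by-image-set (m) and residual (e) effects, given as shares of total variance. Reader-by-image-set variation is zero at first.

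**Step 1: direction, by formula.** Compare two image sets with no true difference, using the difference in latent means as an approximation to the rank test.

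- Pooled readings (30 × 5 = 150 per image set). Variance assumed under independence: 2/(SR). Actual variance: 2(m/S + e/(SR)). Ratio k = R·m + e.
- Subject means. The common reader effect does not vary between subjects. Ratio k = (m + e/R)/(s + m + e/R), which cannot exceed 1. One reader is the case R = 1.
- Approximate true level: P(|Z| > 1.96/√k).

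**Step 2: compare with simulation** (3,000 null runs per row, five readers, r = 0.1 throughout).

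| s, m, e | Pooled k | Pooled level: formula / simulated | Subject-mean k | Subject-mean level: formula / simulated | Signed-rank on subject means, simulated |
|---|---|---|---|---|---|
| 0.5, 0, 0.4 | 0.4 | 0.2% / 0.4% | 0.138 | 0.0% / 0.0% | 5.5% |
| 0.3, 0, 0.6 | 0.6 | 1.1% / 1.6% | 0.286 | 0.02% / 0.03% | 4.6% |
| 0.3, 0.1, 0.5 | 1.0 | 5.0% / 5.6% | 0.400 | 0.2% / 0.3% | 5.0% |
| 0.3, 0.3, 0.3 | 1.8 | 14.4% / 13.5% | 0.545 | 0.8% / 0.9% | 4.7% |
| 0.1, 0.5, 0.3 | 2.8 | 24.2% / 24.6% | 0.848 | 3.3% / 3.6% | 4.8% |

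Worked example, fourth row, pooled: k = 5 × 0.3 + 0.3 = 1.8; 1.96/√1.8 = 1.46; two-sided tail 14.4%.

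With one reader, simulated Mann-Whitney levels over the same rows were 0.7% to 3.7%, against 4.6% to 5.3% for signed-rank.

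A second simulation used cut-points one unit apart and standard deviations for (subject, reader, subject-by-image-set, residual) of (1.0, 0.4, 0.2, 0.5), (0.7, 0.4, 0.5, 0.6) and (0.5, 0.3, 0.8, 0.6). Pooled Mann-Whitney levels were 0.3%, 9% and 23%.

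**Step 3: power.** In the second simulation, with five readers and a shift of 0.5 (half a category), Mann-Whitney on subject means had power 33%, 55% and 48%; signed-rank had 100%, 88% and 59%. At a full-category shift the gap nearly closes: 98-100% against 99-100% with five readers, and 89-97% against 91-100% with one.

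**Step 4: readers who favour different image sets.** Adding a reader-by-image-set share of 0.05 (s = 0.3, m = 0.2, e = 0.35) and treating readers as a sample gave these levels:

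- pooled Mann-Whitney with five readers: 23.2%
- signed-rank on subject means with five readers: 14.4%
- Mann-Whitney with one reader: 19.9%

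In the second simulation, a reader-by-image-set standard deviation of 0.2 raised signed-rank on subject means to 25%, 12% and 9%.

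**Step 5: multiplicity.** Four unadjusted tests at 5% would give 1 − 0.95⁴ = 18.5% family-wise error if independent. The contrasts share image sets, so this is only an illustration.

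**The case against.** The strongest reply is that little hangs on this test. It runs only if the Likert option is chosen. The study is a single-site feasibility study with no stated hypothesis, significance level, power or success threshold; its images do not drive treatment decisions, and the scores can be reanalysed without new data. All of this stands, and it limits the severity. It does not make the test suitable, since Likert scoring is one of two permitted options and this is the only analysis named for it.

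A reader might infer that the planned p-values will overstate significance. The documents do not support that. They do not say that readings will be pooled, or that every reader scores every subject, and five per discipline is a maximum. Even with pooling, the level exceeds 5% only when k is above 1, which depends on variances the plan does not give. Without pooling, and without reader-by-image-set variation, the error is lost power.

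A reader might also take the power gap at half a category as typical. The plan states no expected effect, and the gap is small at a full category.

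Finally, a signed-rank test on reader averages is not a complete cure. Step 4 shows that it is also miscalibrated if readers differ in which image sets they favour and the conclusions are meant for readers in general. This objection stands and shapes the fix.

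**Conclusion.** The concern holds, conditional on the Likert option. Within-subject pairing follows from the plan's own description and does not depend on the simulations. The size of the error does depend on assumptions: the variance components, a 5% level, and full crossing of five readers with 30 subjects. On those, pooled Mann-Whitney runs from about 0.3% to 23-25% at a nominal 5%. On subject means or a single reader it is conservative, at roughly 0% to 4%, when there is no reader-by-image-set variation.

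It would go too far to say that the sample size or a stated error rate is invalid, because the plan states no power or error rate and does not base its 30 subjects on one. This is a should-fix.

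**What to change.** In sections 5.2(3) and 10.1, replace Mann-Whitney with a paired analysis, run separately for oncologists and therapists.

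- **Simple version.** Average over readers within subject and image set. Apply Wilcoxon signed-rank tests to the within-subject differences for the four contrasts of section 2.1 (Ethos breath-hold and Ethos free-breathing, each against fan-beam CT and TrueBeam CBCT). Adjust for multiplicity, for example by Holm, and state that conclusions are conditional on these readers.
- **If results are to generalise beyond these readers.** Fit an ordinal mixed model with image set as fixed effect and random effects for subject, reader, subject-by-image-set and reader-by-image-set.

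The same edit should say whether every reader scores every subject. It should also settle the scale, because no test is named for the ranking branch.

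The cost is a few sentences and slightly more analysis work. No new patients, images or readers are needed. The change is best made before scores are analysed, so that the method is not chosen after seeing them.

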As explained in the objectives below, we expect that the Ethos CBCT will introduce previously unrealized image quality and anatomy visualization for on-couch imaging that will improve the precision of treatment delivery. Should this be the case, the improvement in intra treatment image quality will influence clinical practice on multiple fronts. The potential improvements in precision that come from better on-couch imaging may enable hypofractionation of patient treatment, e.g., compression of a 20+ daily fraction treatment course to 5 fractions, because higher fractional doses can be delivered safely. Improvements in visualization of anatomy resulting from increased image quality may enable accurate online adaptation of a patient's treatment plan in the presence of inter-fraction anatomical change. It may also facilitate development of rapid treatment paradigms without the need for a simulation procedure. For example, a patient with spinal cord compression could both have a treatment plan generated from the Ethos CBCT and then receive treatment on the Ethos platform, reducing time to treatment to one hour instead of one day.

With minimal disruption for participating patients, this study will enable a comparison of (i) the patient's treatment planning fan-beam CT and (ii) the patient's status-quo CBCT on an existing treatment unit with (iii) the high-performance CBCT on Ethos. Image quality of the high performance CBCT will thereby be compared to both a best-case standard (fan-beam) and the status-quo for IGRT to isolate and identify improvements. Image quality will be quantified in terms of contrast-to-noise ratio (CNR), resolution, Hounsfield Unit (HU) accuracy and artifact reduction with a focus on anatomy germane to the image guidance task. A qualitative assessment of the different image datasets will also be performed through feedback from multiple observers (radiation oncologists and radiation therapists). Radiation doses to key treatment targets and organs at risk will be calculated from the high performance CBCTs to determine the suitability of the CBCT images for RT dosimetric planning. Patient experience will be evaluated through questionnaires.

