## 1.2 Risk/Benefit Assessment

### Potential risks of this study:

In routine clinical practice, the standard IGRT workflow may involve multiple CBCT acquisitions during each treatment session to ensure proper patient alignment. Patients

enrolled in this study will undergo two additional research CBCTs (high performance CBCTs on Ethos), both of which will be acquired during a single treatment visit. The radiation dose associated with these two additional CBCTs is approximately 1/5000 to 1/1000 of the dose that the patient will be receiving from the radiation therapy itself. To put this additional dose into perspective, it is helpful to understand that in routine radiotherapy there is inherent and acknowledged uncertainty in the delivered radiation dose. This uncertainty can be 3-5% of the prescribed dose. The dose from the two research CBCTs represents just an additional 1/50th of the already existing uncertainty. Thus, for this patient group, there should be no statistically detectable harm from the two additional CBCTs, e.g., with regard to late effects of the additional radiation.

There is also a potential risk for loss of patient privacy associated with the collection of patient data for this study. This risk will be mitigated by collecting only data that are necessary for the analyses specified in this protocol, by linking data to an anonymized research identifier and by storing data in a secure location to which access is controlled and audited.

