#### 2.2.2 Secondary Objective Metrics

Dose-volume histograms for key target structures and organs at risk will be calculated from the Ethos and TrueBeam CBCT images and compared to those from the existing dosimetric plan for each patient to determine the accuracy of the dosimetric calculations based on the CBCTs.

The patient experience with CBCT image acquisition will be determined through the use of a questionnaire comparing the TrueBeam CBCT image acquisition process to that of the Ethos CBCT process.

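### The planned dosimetry summary (averages and SDs of DVH metrics) discards the within-patient pairing, so it does not reliably show per-patient accuracy or suitability for planning

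*Combined protocol and SAP*

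**What the plan says.** The dosimetric comparison is secondary objective 1 (Section 2.1). Section 1.1 says doses are calculated from the high-performance CBCTs "to determine the suitability of the CBCT images for RT dosimetric planning". Section 2.2.2 says the CBCT-based histograms are "compared to those from the existing dosimetric plan for each patient to determine the accuracy of the dosimetric calculations based on the CBCTs".

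Section 5.2, item 2, describes the procedure. The patient's plan, first calculated on the fan-beam CT, "will be recalculated on both the TrueBeam CBCT and Ethos CBCT datasets using the following process": contours are deformed onto each CBCT, checked by a radiation oncologist and adjusted where needed, and the dose is recalculated. Histograms from the fan-beam plan and the three CBCT-based plans are then compared "in terms of standard dosimetry metrics, i.e., target volume coverage and organ-at-risk sparing".

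The only statistical summary is in Section 10.1: "Dosimetry will be compared using average values of metrics derived from dose-volume histograms and standard deviations of those values". No section defines a within-patient difference, an agreement statistic, a tolerance, or a rule for calling a CBCT accurate or suitable.

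**The concern.** Section 5.2 produces paired data, because the same plan is calculated on several image sets of the same patient. Accuracy and suitability, as Sections 1.1 and 2.2.2 frame them, depend on how far each patient's CBCT value lies from that patient's own plan value. The summary in Section 10.1 does not use that pairing. A mean and an SD per modality are the same whichever value belongs to which patient.

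Two things follow. Over- and under-estimates in different patients cancel in the mean. On the plain reading, the SD is that of the metric values themselves, so it contains differences between patients in anatomy and prescription as well as calculation error. A modality whose individual errors are large but balanced could then give a summary close to that of an accurate one, and the study's own accuracy question would go unanswered although the data to answer it had been collected.

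**Working it through.** The plan has no figure to reproduce here. The 30 subjects are given without an SD, tolerance or power, and this point does not dispute that number.

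**Inputs from the documents.** 30 subjects, with at least 7 each for liver, lung and left breast (Section 10.1); paired recalculation (Section 5.2); mean and SD of metric values as the summary (Section 10.1).

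**Assumptions, because the documents give none.** Plan values normal with mean 95 units and between-patient SD (SDb) of 3, 5 or 10. CBCT value = plan value + unbiased normal error with SD (SDe) of 1, 2 or 3. A deviation of 2 units is used for illustration, with 1 and 3 as alternatives. None of these is a proposed clinical limit. Simulations used 20,000 trials per setting.

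**Step 1: what the summary contains.** Let P and C be a patient's plan and CBCT values, and D = C − P.

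- mean(D) = mean(C) − mean(P). The average bias can be recovered from the planned summary.
- SD(D)² = SD(C)² + SD(P)² − 2·r·SD(C)·SD(P). The within-patient correlation r is not reported, so the spread of individual errors cannot be recovered.

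An exact example with n = 30: shuffling the plan values among patients to form the CBCT column leaves both columns with mean 94.33 and SD 4.31. A perfect CBCT would show the same two numbers. In the shuffled case SD(D) is 5.29, so r = 1 − 5.29²/(2 × 4.31²) = 0.25. The limits of agreement are ±1.96 × 5.29 = ±10.4, and 20 of 30 patients are off by more than 2 units. In the perfect case SD(D) is 0. This is a proof of principle, not a forecast.

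**Step 2: cancellation in the mean.** The SD of the mean error is SDe/√n. For SDe = 2 and n = 30 this is 2/√30 = 0.365, so the median absolute difference in means is 0.674 × 0.365 = 0.25. The share of patients off by more than 2 units is 2 × (1 − Φ(2/SDe)).

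| SDe | Median absolute difference in means (n = 30) | 95th percentile | Patients off by more than 2 units |
|---|---|---|---|
| 1 | 0.12 | about 0.36 | 4.6% |
| 2 | 0.25 | 0.71 | 31.7% |
| 3 | 0.37 | about 1.07 | 50.5% |

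With SDe = 2, the share off by more than 1 unit is 61.7%, and by more than 3 units 13.4%. At n = 7 and SDe = 2, the median absolute difference in means is 0.51 and its 95th percentile about 1.48.

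**Step 3: does the SD give the error away?** Under this model the expected CBCT SD is √(SDb² + SDe²). For SDe = 2:

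| SDb (plan) | CBCT SD | Sample SDs within 10% of each other, n = 30 | n = 7 |
|---|---|---|---|
| 3 | 3.61 | 19.2% | 23.6% |
| 5 | 5.39 | 61.5% | 41.9% |
| 10 | 10.20 | 97.5% | 73.0% |

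The SD carries some information when patients are alike and very little when they differ widely.

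**Step 4: what paired differences would deliver.** The 95% half-width is t/√n for the mean difference and t·√(1/n + 1.96²/(2(n−1))) for each limit of agreement, in units of SD(D). If no patient fails a tolerance, the one-sided 95% upper bound on the failure share is 1 − 0.05^(1/n).

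| n | Mean difference | Each limit of agreement | Upper bound, no failures |
|---|---|---|---|
| 30 | 0.37 | 0.65 | 9.5% |
| 7 | 0.93 | 1.67 | 34.8% |

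**The case against.** The plan does intend a comparison patient by patient. Section 2.2.2 sets each CBCT against that patient's own plan, and Section 10.1 refers back to Section 5 for the analysis. The mean and SD could be read as a group summary of that comparison. If the SDs were meant to be those of within-patient differences, the spread would be visible and only the tolerance would be missing. This narrows the point, but the text refers to metric values and nowhere to differences.

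It is also fair to say that the stakes are limited. This is a secondary objective of a feasibility study, the Ethos images do not drive treatment decisions, and the paired data will exist whichever summary is used. That stands, and it is why no formal test is asked for.

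Four stronger readings are tempting, and the documents do not support them:

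- *The averages say nothing about accuracy.* They show systematic bias (step 1), and error can inflate the SD (step 3). The SD is an unreliable signal, not an absent one.
- *Ethos is never compared with TrueBeam on dose.* Sections 2.2.2 and 5.2 name the existing plan as reference, but the Synopsis has the histograms from all three image sets compared, and objective 1 in Section 2.1 asks for Ethos against TrueBeam.
- *All sites will be pooled.* Section 10.1 neither says so nor promises results by site; it sets minimum numbers per site.
- *The protocol already supplies a tolerance.* Section 1.2 says of routine radiotherapy, "This uncertainty can be 3-5% of the prescribed dose". That concerns delivered dose and puts the imaging dose in perspective. It is not a limit for agreement between calculations.

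**Conclusion.** The concern holds in this form: the stated summary can reveal average bias but does not reliably show per-patient accuracy or suitability, which Sections 1.1 and 2.2.2 set out to determine. That the pairing is lost follows from algebra and needs no assumption. The size does: with unbiased normal error of SD 2 units and 30 subjects, a median difference in means of 0.25 goes with 31.7% of patients off by more than 2 units. The range over error SDs of 1 to 3 is 4.6% to 50.5%. How far the SDs would warn the reader depends on between-patient spread, which the documents do not give.

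A reader might infer that a poor CBCT would be declared accurate under this plan. The documents do not support that, because they contain no acceptance rule. The likelier harm is a reassuring average that leaves the question open.

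**What to change.** Reword Sections 2.2.2 and 10.1 as follows.

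1. Make the summary the within-subject difference, CBCT minus fan-beam plan, for each DVH metric in its own units (some coverage metrics are volumes and cannot be expressed as a percentage of prescribed dose). Do this for the TrueBeam, Ethos breath-hold and Ethos free-breathing sets.
2. For each, report the mean and SD of the differences (or limits of agreement), the median absolute difference and the range, overall and by anatomical site. Read the site results with the precision at n = 7 in mind.
3. Report the proportion of subjects within a tolerance that the study team states and justifies before analysis. It should not be borrowed from the delivered-dose uncertainty in Section 1.2.
4. Make the Ethos versus TrueBeam comparison within subject. Section 5.1 takes the TrueBeam CBCT from the same day, so anatomical change since simulation is largely shared. Report the signed Ethos minus TrueBeam difference, and which of the two lies closer to the plan in absolute terms.
5. State that CBCT-minus-plan differences also contain anatomical change since simulation, contour adjustment and, for the free-breathing set, breathing geometry, so a difference is not by itself a calculation error.
6. Keep the modality averages and SDs as description.

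The cost is a little more analysis and the need to settle a tolerance, and the results may look less favourable than group averages. No further subjects, scans or dose recalculations are needed.
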